All patients will be contacted every 12 weeks ( $\pm$  4 weeks) from the time of the 30-day safety follow-up visit until one year from last patient's first study treatment.

**Statistical methods:** All statistical analyses will be performed using the most recently released and available Statistical Analysis Software (SAS) statistical software, unless otherwise noted. For categorical variables, the number and percent of each category within a parameter will be calculated. For continuous variables, the sample size (n), mean, median, and standard deviation, as well as the minimum and maximum values, will be presented. Missing data will not be imputed unless otherwise stated. There will be a summary of patient disposition, patient demographics, and baseline characteristics. PK parameters will be computed and presented in tables and listings. Plasma concentrations will be presented in graphs for each patient and by cohorts. Latest version of SAS or WinNonlin will be used for the PK analyses.

No formal interim analysis for efficacy will be performed; however, futility analyses will be conducted after 10 patients and, if deemed necessary, 15 patients in cohort A are evaluable for efficacy (i.e., patients should have performed at least one post baseline objective response assessment- *unless there is earlier clear evidence of PD*), as well as cumulative after enrollment of every 10 evaluable patients for efficacy (if deemed necessary) in study Part 3. At each analysis, futility will be evaluated using a Bayesian approach with a non-informative conjugate prior. The decision rule will be to recommend stopping for futility if there is sufficiently low probability (20% or less) that Objective Response Rate (ORR) exceeds the pre-specified (historical) control response of 40%. The primary analysis will be conducted after all enrolled patients reached their 3rd on-treatment scheduled response assessment or have discontinued from treatment. The final analysis will be triggered one year after the last accrued patient's first dose date. In the exceptional

case that after the final analysis a patient(s) might continue to receive study treatment under the protocol, any subsequent data generated from this patient(s) will be summarized in an addendum report to be issued after the last treatment of the last patient.

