To minimize the risk of tumor lysis syndrome (TLS), patients with high tumor burden and/or high circulating lymphocyte counts should be adequately hydrated prior to the infusion. Serum chemistry assessments will be conducted at each visit, including at Day 2 and Day3 after the first two cycles.

As pneumonitis has been reported with the use of ADCs, including one fatal case in a patient receiving treatment with Debio 1562, despite the absence of a causal dose and temporal relationship with Debio 1562, the current protocol excludes the enrollment of patients with current diagnosis of interstitial lung disease or with clinical history of severe parenchymal lung disorders.

In an effort to minimize the risk of Coronavirus Disease 2019 (COVID-19) infection for patients participating in the study, the sponsor decided that in the interest of patient safety it is best to allow to switch patients who are on the QW Debio 1562 dosing regimen to the Q3W. The switch from the QW to Q3W regimen is not expected to result in any detrimental effect on safety or efficacy for these patients, based on recent analysis of preliminary study data.

This will reduce the number of visits to the hospital. Therefore, reducing the exposure of patients to a potential risk of contamination, while ensuring adequate treatment. The measure taken will also reduce the burden at the trial sites during the pandemic.

As of April 14, 2020, three patients are on treatment with QW dose regimen. All were granted permission to switch to the Q3W regimen by Study Sponsor in the best interest of the patients. Study enrollment has been completed. In addition to the specific risk minimization measures, safety will be closely evaluated throughout the study until the 30-day safety follow-up visit. The safety assessments include AE reporting, laboratory assessments, electrocardiogram (ECG), physical exams, and vital signs. An IDMC will monitor the safety data regularly throughout the study, and provide recommendations at the pre-defined timepoint based on the data (see [Section 4.1.3.2](#)).

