### **5.8.4. Monitoring and Management of Rituximab-induced Progressive Multifocal Leukoencephalopathy (PML)**

John Cunningham virus infection resulting in PML and death can occur in patients receiving rituximab and it has been shown to occur more frequently in patients who received rituximab in combination with chemotherapy or as part of a hematopoietic stem cell transplant. Most cases of PML were diagnosed within 12 months of their last infusion of rituximab. Consider the diagnosis of PML in any patient presenting with new-onset neurologic manifestations. Evaluation of PML includes, but is not limited to, consultation with a neurologist, brain magnetic resonance imaging (MRI), and lumbar puncture. If a positive diagnosis of PML is made, rituximab should be discontinued.

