### **5.8.7. Monitoring of Rituximab-induced Serious Infections**

Serious, sometimes fatal bacterial, fungal, or viral (new or reactivated) infections have been shown to occur in patients receiving rituximab, during therapy and up to one year following the completion of rituximab-based therapy. Reported new or reactivated viral infections include cytomegalovirus, herpes simplex virus, parvovirus B19, varicella zoster virus, West Nile virus,

and hepatitis B virus (HBV) and hepatitis C virus. Patients should be monitored for signs and symptoms of infections. Rituximab should be discontinued in patients experiencing serious infections; patients should receive anti-infective therapy as per institutional guidelines.

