#### **5.8.7.1. Monitoring and Management of Rituximab-induced HBV Reactivation**

HBV reactivation with fulminant hepatitis, hepatic failure, and death has been shown to occur in patients with hematologic malignancies who received rituximab. The median time to diagnosis of hepatitis was approximately four months following the first dose of rituximab and approximately one month after the last dose. Known HBV carriers can participate in this study provided they are HBsAg PCR negative and are receiving antiviral therapy. Rituximab should be discontinued in patients who develop viral hepatitis; patients should receive appropriate treatment including antiviral therapy as per institutional guidelines.

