## 9. ASSESSMENT OF SAFETY

### 9.1. Recording Adverse Events and Serious Adverse Events

AEs (including SAEs) will be documented on the AE eCRF and monitored continuously throughout the study from the time informed consent is obtained until 30 days after the patient's last study treatment or until the event has resolved or stabilized or an outcome has been reached, whichever comes first.

For patients who discontinue study treatment due to a study-related AE, the reporting time-period may be extended. These patients must be followed at least once a week for four weeks, and subsequently at 4-week intervals until resolution or stabilization of the AE or laboratory abnormality, whichever comes first ([Section 5.10.1](#)).

If the Investigator considers it necessary to report an AE considered study drug related in a patient occurring after the end of study, he or she should contact the Sponsor to determine how the AE should be documented and reported.

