## 9.2. Recording Adverse Events

### 9.2.1. Reporting Serious Adverse Events

Any SAE, regardless of relationship to study medication, which occurs in a patient from the time informed consent is obtained until 30 days after the last study treatment, should be recorded by the clinical site on an SAE Report form. This reporting requirement also includes SAEs that are attributed to a study procedure performed during the screening period (from the time of consent until the time of first dose of study treatment). The SAE must be completely described on the patient's eCRF, including the judgment of the Investigator as to the relationship of the SAE to the study treatment (Debio 1562 and rituximab). The Investigator will promptly supply all information identified and requested by the Sponsor (or Contract Research Organization [CRO]) regarding the SAE.

The Investigator must report the SAE to the Sponsor's Medical Director or designee. The SAE Report form must be completed and submitted within 24 hours of the Investigator's learning of the event to the contact persons listed in the Study Manual provided to each site and maintained in the Investigator study files. Any follow-up information must also be completed on an SAE Report form and submitted to the same contacts.

When reporting SAEs, the following additional points should be noted:

- The underlying diagnosis or syndrome should be reported as the primary SAE term, rather than the signs or symptoms (signs and symptoms may be described in the narrative).
- Progression of disease should not be reported as an SAE; any serious medical event/condition that results from progression of underlying disease should be reported as the SAE.
- Death should not be reported as an SAE, but rather as an outcome of a specific SAE, unless the event preceding the death is unknown. In these exceptional cases, death may be used as an event term. If an autopsy was performed, the autopsy report should be provided.

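### Mandatory AE and SAE recording ends about 30 days after last treatment, so a new non-fatal related SAE after that has no required collection, although the protocol itself describes rituximab risks up to a year after therapy

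*Protocol*

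**What the plan says.** The mandatory window closes at about 30 days, but its end point is worded in two ways.

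- Protocol 9.1 has AEs, including SAEs, recorded "from the time informed consent is obtained until 30 days after the patient's last study treatment". Section 9.1.1.1 repeats this. Section 9.2.1 requires a report of any SAE, whatever its relationship, "which occurs in a patient from the time informed consent is obtained until 30 days after the last study treatment".
- Protocol 1.9 states: "In addition to the specific risk minimization measures, safety will be closely evaluated throughout the study until the 30-day safety follow-up visit". Section 5.11 also ends the safety period at the final safety visit. Appendices A to C give that visit a window of 30-42 days.
- The TEAE definition (protocol 9.1.1.1, SAP 10.3.1) stops 30 days after the last dose of either drug.

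The protocol also describes when the late rituximab risks appear.

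- Section 5.8.7: serious, sometimes fatal infections occur "during therapy and up to one year following the completion of rituximab-based therapy".
- Section 5.8.4: "Most cases of PML were diagnosed within 12 months of their last infusion of rituximab".
- Section 5.8.7.1: the median time to diagnosis of hepatitis is about four months from the first rituximab dose and "approximately one month after the last dose".

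Contact with patients does not stop at the safety visit. The Synopsis (treatment and study duration) says "All patients will be contacted every 12 weeks", give or take 4 weeks, from that visit until one year after the last patient's first treatment. SAP 10.2.2 and 10.2.4.4 list what follow-up yields: PD status, survival status and new anti-cancer therapy. Neither document asks for new SAEs there.

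**The concern.** Safety and tolerability of the Debio 1562 regimens in combination with rituximab is the first-listed primary objective (protocol 2.1.1). The protocol names three kinds of serious event that can arise after its own recording window, and follows patients beyond that window without asking about them. The events matter in this population: section 3.1 admits HBsAg-positive, PCR-negative patients who are on antivirals, and section 10.6.3 makes hepatic damage a point of special focus for both committees. Section 3.1 also requires contraception for 12 months after the last rituximab dose, so the protocol already works with a year-long horizon for another purpose.

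At stake is the completeness of the safety record for related SAEs that do not kill the patient. Such an event could go unrecorded. If reported voluntarily, it would fall outside the TEAE tables and could appear only as a flagged non-TEAE in a listing (SAP 10.3.1).

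**Working it through.** The plan gives no figure on this point to reproduce. The check compares windows and latencies, with illustrative arithmetic.

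**1. What reaches the database after the window?**

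| Event after the window | Route in the documents | Required or scheduled? |
|---|---|---|
| Death, any cause | SAP 10.3.2: deaths beyond 30 days summarised and listed; cause tabulated as PD, AE, Other or Unknown | Yes |
| AE that led to stopping treatment, if study-related | Protocol 9.1: reporting period may be extended, with weekly then 4-weekly follow-up to resolution | Yes for the known event; extension of reporting is permissive |
| Related AE after the end of study | Protocol 9.1: investigator contacts the sponsor if he or she considers it necessary | Discretionary |
| New non-fatal related SAE between the 30-day visit and the end of study | None found | No |

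The third route does not clearly cover the fourth row. Section 11.10 defines the end of study for the whole trial (the later of the last safety visit or one year from the last accrued patient's first visit), not for each patient.

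**2. Hepatitis.** By definition of a median, about half of diagnoses come later than about one month after the last rituximab dose. For other cut-offs, assume exponential times from the last dose, with the share after day d = 2^(-d/m) and m = 365.25/12 = 30.4 days:

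- d = 30: 2^(-30/30.4) = 0.505
- d = 42: 2^(-42/30.4) = 0.384

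Varying the median from 21 to 45 days gives 37-63% after day 30 and 25-52% after day 42.

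One refinement: the clock runs from the last study treatment. A weekly-schedule patient who receives the Day 15 dose of the final cycle had rituximab 14 days earlier. The window then closes 44 days (30 + 14) or 56 days (42 + 14) after rituximab, and the shares fall to 2^(-44/30.4) = 0.37 and 2^(-56/30.4) = 0.28.

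**3. Serious infections and PML.** A 30-42 day window covers 30/365.25 = 8.2% to 42/365.25 = 11.5% of a 12-month period. This is calendar time only. The protocol gives no distribution within the year, so the share of events missed cannot be derived.

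**4. Follow-up without SAE collection.** Take the last-enrolled patient with six undelayed cycles. The last rituximab dose falls 5 x 21 = 105 days after Cycle 1 Day 1, and contact runs to day 365.

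- Contact after the last rituximab dose: 365 - 105 = 260 days.
- Of which without mandatory SAE collection: 260 - 30 = 230 days, or 260 - 42 = 218 days.
- Weekly schedule, last dose on day 105 + 14 = 119: 365 - 119 - 30 = 216 days, or 365 - 119 - 42 = 204 days.

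A patient who started at least 105 days before the last one would have contact for a full year after rituximab (260 + 105 = 365).

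**5. The two end points.** If the visit takes place on day 40, an SAE with onset on day 35 is inside sections 1.9 and 5.11 but outside section 9.2.1.

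**The case against.** The strongest reply has four parts.

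- **Routes exist beyond day 30.** Late deaths are captured with a cause, section 9.1 can extend reporting, and an investigator can contact the sponsor. The safety visit, which may fall as late as day 42, includes AE evaluation and chemistry with ALT, AST and bilirubin. This stands, and it limits the gap to new, non-fatal events. It does not close it.
- **The late risks belong to rituximab, a marketed product.** Sections 5.8.4 and 5.8.7 describe rituximab and state no late risk for Debio 1562. This stands. The primary objective nevertheless concerns the combination, and section 9.1.1.2 asks for causality for each drug and for the combination.
- **Hepatitis risk is reduced by design**, through HBsAg screening, exclusion of active hepatitis, the PCR condition and antiviral prophylaxis. This lowers the expected number of cases. It does not change the share diagnosed after the window.
- **The calendar.** Enrolment, which section 5.5 ties to a first dose, was complete by Amendment 6, which the SAP dates 2020-04-24. Contacts end one year after the last first dose, hence by about April 2021, and SAP version 3.1 is dated 2021-05-07. If that schedule was kept, no planned contact remains. This restricts what can still be done prospectively; it does not make the written rule sound.

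A reader might infer that late related SAEs are systematically missed, that a 30-day window loses over 90% of them, or that the IDMC would be left unaware of a signal. The documents support none of these. Discretionary reporting remains possible, 8.2% is a share of time and not of events, and enrolment was already complete. Nor can a count be given: neither document states a rate for these late events, so any number would only restate an assumption.

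**Conclusion.** The point holds in a limited form. A new non-fatal SAE related to either drug, arising between a patient's 30-day visit and the end of study, is not required to be reported, is not asked about at any scheduled contact, and lies outside the TEAE analysis. The accurate description is that such events are not systematically collected.

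The only quantity the documents support is for hepatitis: roughly half of diagnoses after day 30, from the protocol's own median. The figure of about 38% after day 42 rests on the exponential assumption, and both shares are lower for weekly-schedule patients, whose window runs from a later dose. For PML, 12 months covers most cases and is not an upper limit. The number of events missed is unknown. This is a low-cost improvement to the completeness of the primary safety record. It does not show that the reported toxicity profile would be materially wrong.

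**What to change.** In protocol 9.1 and 9.2.1, with the sentence in 1.9 aligned:

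- Keep the 30-day window for all AEs, and leave the TEAE definition unchanged.
- State one end point, reconciling 30 days with the 30-42 day visit.
- Require that any SAE the investigator considers related to Debio 1562 or rituximab, including related serious infection, viral hepatitis or PML, with onset after that window and up to the end of study, be asked about at the existing 12-weekly contacts and reported.

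In SAP 10.3.1, add a by-cohort listing or table of these late related SAEs, separate from TEAEs, flagging those with onset after new anti-cancer therapy, where attribution is harder.

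The cost is protocol and eCRF wording, a few questions at contacts already planned, one extra output, some added reporting work and a slightly less favourable safety summary. No visit is added and the TEAE tables do not change. Late enrollees would still have less than a full year of cover, because contacts end one year after the last patient's first dose. Where contacts have already ended, the clinical study report should state that non-fatal related SAEs after the 30-day window were not systematically collected, and list any that were reported voluntarily.

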## **1.10. Amendment History**

### **1.10.1. Amendment 1**

The reasons for amending the protocol are as follows:

1. The document was edited to clarify protocol procedures, improve internal consistency and, consequently, readability and understanding.
2. Some of the details were removed from the synopsis as they are detailed in the main body of the protocol, thereby reducing duplication and risk of error.
3. The Safety Review Committee composition and function is described in the synopsis as it is referenced early in the document.
4. The following sections of the protocol were revised and edited for clarification purposes:
  - a. The rationale for the starting doses of Debio 1562 (formerly IMGN529) and rituximab

- b. The rationale for the study plan
- c. The Study Design
- d. Study Drug Administration
- e. Management guidelines for infusion reaction
- f. PK Assessments
- g. ECG procedures
- h. Radiologic imaging and tumor response assessment guidelines

5. The objectives and endpoints were edited for clarity and one of the exploratory objectives was expanded [REDACTED]; the corresponding endpoint was revised accordingly.

6. Revisions were made to the Inclusion and Exclusion Criteria.

7. The Toxicity Management Guidelines, including the sections of the protocol describing dose modifications and AE assessments, were revised to improve internal consistency and to define “Dose Modifying Events”.

8. The guidelines for patient discontinuation and collection of subsequent anti-cancer therapy were revised.

9. The hematology and serum chemistry assessments were streamlined.

10. The section of the protocol detailing the study activities was deleted entirely.

11. The section of the protocol describing records retention was streamlined.

12. Missing references were added to the protocol.

13. The Schedule of Events was revised.

14. The Ann Arbor Staging Criteria (with Cotswold Modifications) were added to the protocol.

#### **1.10.2. Amendment 2**

The protocol was amended for administrative reasons as the ownership of IMGN529 was transferred from ImmunoGen Inc. to Debiopharm International S.A.

As a result, the following changes were made:

- The Sponsor name and address were updated
- The contact medical director's name and address were updated
- Product identifier was changed from IMGN529 to Debio 1562 throughout the document
- Study number was changed from 0302 to Debio 1562-201 throughout the document

#### **1.10.3. Amendment 3**

The reasons for amending the protocol are as follows:

- To confine the patient population to those with relapsed DLBCL in study Part 2 (cohorts A and B) and study Part 3, to have a more homogeneous population for data analysis.

- To add an arm to investigate a new QW Debio 1562 dosing schedule (cohort B) while maintaining the current Q3W Debio 1562 dosing arm (cohort A), without increasing the cumulative Debio 1562 dose currently allowed in the protocol (i.e., 0.7 mg/kg – 1.0 mg/kg Q3W).
- To change the fixed study design to an adaptive design in order to utilize the generated data to establish a dosing regimen associated with optimal benefit-risk.
- To add blood sampling time points to improve evaluation of PK disposition.
- [REDACTED]
- To add HRQoL assessment.

#### **1.10.4. Amendment 4**

The main reason for amending the protocol was to reflect the following changes requested by regulatory health authorities during the review process of the previous protocol.

- To update eligibility criteria to exclude patients currently presenting interstitial lung disease, diffuse parenchymal lung disease, or with a past history of severe/Grade 3 parenchymal lung disorder
- To extend the period of monitoring to 4 hours after completion of the rituximab infusion for the first cycle
- To introduce a new section of risk minimization measures for the expected serious adverse reactions

In addition, [Section 5.9](#) was revised for clarification purposes. Some minor changes are also included in other sections of the protocol for clarification and to improve consistency.

#### **1.10.5. Amendment 5**

The main reason for amending the protocol is to address the potential for exceptional individual patients' study treatment prolongation beyond 6 cycles, provided the patient is benefitting from the study treatment and after discussing and agreement with the Study Sponsor.

Furthermore, this protocol amendment also addresses the following:

- To clarify study treatment duration and the conditions under which treatment duration may be prolonged for patients who exceptionally continue study treatment beyond 6 cycles ([Section 4.1.1](#))
- To clarify the frequency and imaging modality of radiologic tumor response assessments for patients who exceptionally continue study treatment beyond 6 cycles ([Section 8.14](#))
- To clarify last timepoint of PK, Immunogenicity [REDACTED] Assessments at Cycle 7 Day 1 (C7D1), instead of End of Treatment (EOT) visit and with no additional samples taken at 30-day follow-up visit for patients who exceptionally continue with treatment beyond 6 cycles ([Sections 6.1](#); [Section 6.2](#); [Section 6.3](#); [Appendix E](#), [Appendix F](#) [REDACTED])

- To clarify last timepoint of assessments of HRQoL at C7D1: instead of EOT visit and with no additional HRQoL assessment to be completed at 30-day follow-up visit for patients who exceptionally continue with treatment beyond 6 cycles (Section 8.8)
- To clarify that primary analysis will be conducted after all enrolled patients reach their 3rd on-treatment scheduled response assessment or have discontinued from treatment. The final analysis will be triggered one year after the last accrued patient's first dose date. In the exceptional case that after the final analysis a patient(s) might continue to receive study treatment under the protocol, any subsequent data generated from this patient(s) will be summarized in an addendum report to be issued after the last treatment of the last patient (Section 10).
- APPENDICES A-C: Schedule of events were revised for clarification purposes.
- Clarification was made regarding the separate tubes used for blood draw for PK assessment and for anti-drug antibodies (ADA).
- Clarification that the potential immunogenicity against rituximab will be assessed.
- Some minor changes are also included in other sections of the protocol to improve clarity and consistency.

Based on the changes above, this amendment is considered substantial, requiring approval by Ethics Committees and Regulatory Authorities before implementation.

